13.1.2 Changes to the protocol text

All sections of the protocol affected by the amendment are shown below. Deleted text is ~~crossed out~~ and added text is underlined. Corrections of typographical errors or editorial corrections are not highlighted.

Synopsis, Diagnosis and main criteria for inclusion

- Absence of cervical carotid atherosclerotic stenosis greater than ~~or equal to~~⁴⁶ 50% or occlusion, and

⁴⁶ Symbols are used in the text (ie, \geq and $>$)

- No atrial fibrillation after \geq 24-hour cardiac rhythm monitoring (at least 20 hours acceptable), and
- No intra-cardiac thrombus on either transesophageal or transthoracic echocardiography, and

Synopsis, Methodology

Patients who fulfill all inclusion and none of the exclusion criteria after giving informed consent will be randomly allocated 1:1 to either rivaroxaban 15 mg or aspirin 100 mg orally once daily. Randomization will be stratified by country and age <60 and ≥ 60 years. ~~No more than 10% of the total patient population will be randomized into the age group <60 years.~~

Synopsis, Number of subjects

The number of patients enrolled in the total study may be adjusted or enrollment in the age group 50-59 years may be stopped based on a blinded review of the observed overall event rate of confirmed primary efficacy outcomes during the study.

Synopsis, Plan for statistical analysis

There will be ± 2 formal interim ~~analysis~~ analyses to assess efficacy and stop for overwhelming superiority, which will occur when approximately 50% and 67% of the planned primary efficacy outcomes have accrued.

Table of procedures

	Screen	Random	Treatment Phase						Washout
	V1	V2	V3	V4	V5	V6	V7-V [∞]	EOT ^a	Safety Visit
Timelines	-4-6 to 0 wks ^b	0	1 Mo	3 Mo	6 Mo	12 Mo	every 6 Mo	End of Treat	1 Mo post EOT
Visit Window (weeks)			±1	±4	±4	±4	±4		±1
Type of Visit	Visit	Visit	Visit _L	☎	Visit	Visit	Visit	Visit	☎
.....									
EQ-5D MoCA, DSS, and SAGE		• •			•	•	•	•	

Abbreviations: EOT = end of treatment; Mo = month; V = visit, ☎ = telephone contact; eGFR = estimated glomerular filtration rate; ConMeds = Concomitant medications; MoCA = Montreal Cognitive Assessment; DSS = Digit Symbol Substitution test; SAGE = Standard Assessment of Global-Activities in the Elderly; EQ-5D = European Quality of Life-5 Dimensions questionnaire; SAE = serious adverse event; TIA = transient ischemic attack; MI = myocardial infarction

- a End of treatment visit is to be performed within the trial close-out window before the end of the study (efficacy cut-off date) or once the patient has permanently discontinued study medication and when no further visits at the site will be performed
- b Screening visit can be the same as randomization visit, if all required tests for eligibility criteria are available at screening visit. Maximum screening period -4-6 weeks.

.....

k For definition see Section 7.6.1.4. In case of recurrent stroke to be done at 7 days post stroke or at discharge from hospital in case this occurs before 7 days and again at 3-6 months post stroke

L Patients who are at a rehabilitation or other clinic at the time of the 1 month visit (Visit 3), more flexibility will be allowed and this visit can be performed as a phone call instead of an onsite visit.

.....

Section 1.3 Studies assessing the efficacy of anticoagulation for secondary prevention of embolic stroke of undetermined source, last sentence of 3rd paragraph

In addition, in the PICSS study, 260 98 participants with a patent foramen ovale, the primary outcome (2 year rate of recurrent ischemic stroke or death) was halved in those assigned to warfarin (9.5% warfarin vs. 17.9% ASA).

Section 4.1 Overview, 4th and 5th paragraphs

Patients will be enrolled randomized as early as possible after the required diagnostic evaluation is complete and eligibility criteria are fulfilled. The goal is that the majority of patients are enrolled within 3 months, and fewer patients between 3 and 6 months.

Randomization will be stratified by country and age <60 and ≥60 years. ~~No more than 10% of the total patient population will be randomized into the age group <60 years, as patients with <60 years have a lower risk for recurrent stroke.~~ Patients < 60 years will need to have at least one risk factor such as stroke (includes covert/silent strokes on neuroimaging) or TIA prior to index stroke, diabetes, hypertension, current tobacco smoker or ~~and~~ heart failure.

[figure not shown]

Figure 4-1

Section 5 Study population

This Phase III, multi-national, study will be conducted in ~~25 to 30~~ approximately 30 countries worldwide in approximately 7000 patients recruited primarily from hospital-based stroke units.

Section 5.1.1 Inclusion criteria

1. Embolic stroke of undetermined source (ESUS) defined as:
 - Recent ischemic stroke (including TIA with positive neuroimaging) visualized by brain CT or MRI that is not lacunar (i.e., lacunar infarcts are subcortical infarcts ≤ 1.5 cm in the territory of middle cerebral artery or pons; infarcts involving the cerebellum or lateral medulla are not considered as lacunar infarcts). Patients with multiple simultaneous acute lacunar infarcts on DWI imaging may be included. In case of embolic large artery occlusions clearly documented on angiography who undergo successful recanalization, visualization of infarct on neuroimaging is not mandated, and
 - Absence of cervical carotid atherosclerotic stenosis (or vertebral and basilar artery atherosclerotic stenosis in case of posterior circulation stroke), that is greater than ~~or equal to~~ ⁴⁷ 50%, or occlusion in arteries supplying the area of ischemia in CT or magnetic resonance (MR) angiography or conventional angiography or ultrasound, and
 - No history of AF, no documented AF on 12-lead electrocardiogram (ECG) or episode of AF lasting 6 minutes or longer detected after ≥ 24 -hour cardiac rhythm monitoring (Holter or telemetry; at least 20 hours acceptable), and
 - No intra-cardiac thrombus on either transesophageal or transthoracic echocardiography, and

...

⁴⁷ Symbols are used in the text (ie, \geq and $>$)

4. Age ≥ 18 50 years (~~or respective country specific legal lower age limit if this is >18 years~~)
5. For patients with age < 60 50-59 years at least one of the following risk factors: stroke or TIA prior to index stroke (includes covert/silent strokes on neuroimaging), diabetes, hypertension, current tobacco smoker ~~and~~ or heart failure.

Section 5.1.2 Exclusion criteria

2. If imaging of intracranial arteries is performed by CT or MR angiography or transcranial Doppler: greater than ~~or equal to~~⁴⁸ 50% luminal stenosis or occlusion in arteries supplying the area of ischemia
9. Active bleeding, major bleeding within last 6 months, ~~history of primary intracranial hemorrhage~~ or high risk for serious bleeding contraindicating anticoagulant or antiplatelet therapy or history of primary intracranial hemorrhage

Section 5.2 Discontinuation of patients from study treatment, 2nd, 3rd, and 8th paragraphs

Patients may discontinue study medication at their own request and without giving reasons (even though providing a reason is encouraged), based on the investigator's judgment, if the patient is pregnant, or at the request of the sponsor (exceptional circumstances). In case a patient is diagnosed with atrial fibrillation with an episode of at least 6 minutes during the study trial medication must be stopped (see section 6.9.2)....

In case of a temporary study medication ~~discontinuation~~ interruption for any reason, study medication will be restarted as soon as medically justified in the opinion of the investigator. There is no defined maximum limit for temporary treatment interruption.

....

~~Patients who permanently discontinue the study for any reason will not be reactivated.~~

Section 6.3 Treatment assignment, sentence deleted

~~No more than 10% of the total patient number will be randomized into the age group < 60 years.~~

Section 6.5.1 Emergency unblinding by the investigator

Unnecessary unblinding should be avoided and should only be undertaken by the investigator or the treating physician when it is essential for the patient's safety. In such a situation, the investigator will be able to unblind the patient via the ~~IXRS system~~ country toll-free help line.

Section 6.7 Treatment compliance

First dose, last dose, and any dose interruptions of study medication due to AEs, study outcome events, or of >7 days for any other reason will be reported in the eCRF.

Section 6.9 Prior and concomitant therapy

⁴⁸ Symbols are used in the text (ie, \geq and $>$)

No specific concomitant medications are prohibited other than strong inhibitors of both CYP3A4 and Pgp inhibitors. This includes human immunodeficiency virus protease inhibitors and the following azole antimycotics agents: ketoconazole, itraconazole, voriconazole, or posaconazole, if used systemically. However, fluconazole is allowed.

In addition, concomitant use with antiplatelets and anticoagulants is outlined in the sections below.

Section 6.9.2 Guidance for management of participants who have atrial fibrillation identified during the study

If a patient is diagnosed with AF during the study that requires oral anticoagulation according to the investigator's judgment, the patient will stop double blind study medication. Per protocol, study medication must be permanently discontinued if AF is seen in a 12-lead ECG or if an AF episode of greater than or equal⁴⁹ to 6 minutes is identified during cardiac monitoring.

Section 7.1.2.1 Visit 1 (screening)

Visit 1 will be used to assess the eligibility of the patient. After obtaining signed informed consent, the investigator will review the diagnostic tests required to diagnose ESUS. All diagnostic assessments for ESUS ~~must~~ should be completed before the screening visit. If prolonged cardiac rhythm monitoring and/or echocardiography are not performed at time of screening, this can be done during the screening period.

The screening period will be 6 weeks maximum.

Section 7.1.2.2 Visit 2 (randomization visit)

Outcomes research questionnaires (Section 7.6.1) will be completed by the patient:

- European Quality of Life-5 Dimensions (EQ-5D) Questionnaire
- Montreal Cognitive Assessment (MoCA)
- ~~Digit Symbol Substitution (DSS) test~~
- Standard Assessment of Global-Activities in the Elderly (SAGE) questionnaire

Section 7.1.2.3 Regular study visits (visits 3 and onward), 1st, 4th, 5th and 6th paragraphs

Patients will return to the study clinic at 1 month, 6 months, and then every 6 months. Patients who are at a rehabilitation or other clinic at the time of the 1 month visit (Visit 3), more flexibility will be allowed and this visit can be performed as a phone call instead of an onsite visit. At 3 months, the patient will receive a telephone call to obtain safety and outcome data and reinforce adherence to study medication and to avoiding non-study ASA.

...

Concomitant medications and weight will be collected once per year. If an SAE or study outcome event is reported, the use of any additional ConMeds should be recorded at that time

⁴⁹ Symbols are used in the text (ie, > and ≥).

The outcomes research questionnaires (MoCA, ~~DSS~~, and SAGE) will be completed by the patient at the 1 year visit only. The EQ-5D will be completed every 6 months.

If a recurrent stroke is reported, the modified Rankin Score is to be assessed at 7 days post stroke or at hospital discharge, if this occurs before 7 days, and again at 3-6 months post stroke. The modified Rankin score is also to be recorded at 1 year after stroke.

Section 7.1.2.4 End of treatment (EOT) visit

~~When the sponsor announces~~ Within the trial close-out window prior to the end of the study (efficacy cut-off date), all patients must return to the clinic within 6 weeks in order to make a final assessment. In addition, for patients that permanently discontinued study medication and when further follow-up will no longer be done by site visits and rather by phone or third party contact, the patient will be encouraged to come for the EOT visit as soon as possible after discontinuation of study medication. For these patients a final vital status and outcome events will be collected during the trial close-out window. At this EOT visit, study procedures will include the collection of efficacy and safety outcome data, (S)AEs, vital signs, ConMeds, EQ-5D, MoCA, ~~DSS~~ and SAGE questionnaires, and modified Rankin score. In addition, the study staff will collect the patient's empty and unused study medication bottles to allow final drug accountability and compliance checks.

Section 7.5.1 Primary safety variable

- Symptomatic bleeding in a critical area or organ (intracranial, intraocular, intraspinal, pericardial, retroperitoneal, intraarticular, or intramuscular with compartment syndrome), and/or

Section 7.5.3.2 Adverse event reporting, 3rd bullet

- All bleeding events including fatal bleeding will be captured in the eCRF (Bleeding page). Serious adverse events which are bleeding terms will not be reported to the sponsor's PV Department in an expedited manner. Symptomatic intracerebral/intraparenchymal hemorrhages as well as symptomatic subarachnoid hemorrhages will be captured as bleeding and as stroke. All subdural/epidural hematoma and asymptomatic intracranial bleeding are only reported as bleeding.

Section 7.5.3.4 Intensity of an adverse event, action taken, and outcome

Any action on study treatment to resolve the AE is to be documented as: study drug withdrawn, interrupted, ~~dose reduced~~, dose not changed, ~~dose increased~~, not applicable, or unknown.

Section 7.6.1.3 Montreal Cognitive Assessment, ~~Digit Symbol Substitution test~~, and Standard Assessment of Global-Activities in the Elderly

The MoCA ~~and DSS~~ will be included in the study to assess cognition and the SAGE questionnaire will be used to assess functional outcome. These tests and questionnaires will be administered at Day 0 (randomization), 1 year, and at the EOT visits. The patients will be asked to independently complete the MoCA ~~and DSS~~ tests to the best of their ability. Otherwise, the reason for not completing must be documented. The SAGE questionnaire may be completed with the help of the study staff.

Section 7.6.1.4 Modified Rankin Score

In addition to the regular assessments at screening, 1 year, and EOT, the Modified Rankin Score will be assessed by the investigator at 7 days or at discharge, if this occurs before 7 days, and again at 3-6 months after a recurrent stroke.

Section 8.5 Planned interim analyses

The IDMC will monitor the study for greater than expected efficacy and for safety. There will be ± 2 formal interim ~~analysis~~ analyses to assess efficacy, which will occur when approximately 50% and 67% of the planned primary efficacy events have accrued. ~~The study may be stopped early, IDMC may recommend early study termination at these interim analyses~~ if there is overwhelming superiority of rivaroxaban ($p < 0.0001$ ~~$Z > 4$~~) for efficacy (e.g., following the conservative Haybittle-Peto approach). Also, secondary efficacy and safety will be considered. The study will be stopped early if the totality of data suggests an overwhelming benefit of rivaroxaban over ASA.

The IDMC has the flexibility to initiate further interim analyses after the first formal efficacy analysis at 50 %, if deemed appropriate. Given the conservative nature of the monitoring guidelines used in the trial, no adjustment of the significance level for the final analysis is required.

The execution of the interim analyses and decision rules will be specified in the IDMC charter ~~and the SAP for the interim analysis~~.

Section 8.6 Determination of sample size, 3rd paragraph

The number of patients enrolled in the total study may be adjusted or enrollment in the age group 50-59 years may be stopped based on a blinded review of the observed overall event rate of confirmed primary efficacy outcomes during the study

Section 9.1 Data recording, 2nd paragraph

Data of 'only screened patients' will be recorded ~~at least~~ as source data, as far as the reason for ~~the premature discontinuation (reason for not randomizing the patient into the study)~~ is identifiable. At minimum, data to be recorded in the eCRF are demographic information (patient number, date of birth/age, sex, race and ethnicity), the reason for ~~premature~~

~~discontinuation screening failure~~ and date of last visit. These data will be transferred to the respective database.

Section 14.1.1 MRI substudy, 2nd, 3rd, and 7th paragraphs

The primary objective of this substudy is to determine the effect of rivaroxaban compared with aspirin on MRI-defined covert and clinical infarcts (i.e. all incident infarcts) in individuals with a recent ESUS. ...

Secondary objectives will be to determine the effect of rivaroxaban compared to aspirin for reducing covert ~~and clinical infarcts (i.e. all incident infarcts)~~, the progression of volume of white matter hyperintensities (WMH), functional decline (SAGE), and cognitive decline (ÐSS, MoCA) in the patients with recent ESUS enrolled in this substudy.

...

Two MRIs will be required:

- Baseline: within 7 days of randomization if the patient is randomized within 30 days of the index event or from 7 days before to 30 days after randomization, if the patient is randomized >30 days after the index event. The MRI for the index event may qualify as the baseline MRI, if the imaging was performed within 7 days ~~of~~ before randomization. In the event of a technically unsatisfactory scan as determined by the core laboratory, the site will have 30 days from notification by the coordinating center to repeat the scan.
- Follow-up: within 30 days of EOT visit in individuals who have not experienced a symptomatic stroke prior to EOT or within 30 days of a symptomatic stroke.

14. Appendices

14.1 Substudies

Two substudies are planned at selected sites. Participation in the substudies is not a requirement. The substudies do not necessarily need to be conducted at the same sites and in the same patients.

Conduct of these substudies is contingent on review and approval by the appropriate Health Authorities and the site's IRB or EC. Patients must sign separate ICFs for participation in these substudies.

14.1.1 MRI substudy - amended

Covert ischemic strokes are defined as strokes not identified clinically at the time of their occurrence but resulting in radiologic evidence of brain infarction. Covert strokes are frequent with a prevalence of 20% at the age of 65 years and are 5 times as common as symptomatic strokes.(30,31) Covert strokes may be manifested as subtle cognitive decline, loss of independence, gait impairment, and falls. The post stroke population is characterized as having a high incidence of these covert infarctions (4% to 24% from 3 cohort studies) and subsequent cognitive and functional impairment.(32-34)

The primary objective of this substudy is to determine the effect of rivaroxaban compared with aspirin on MRI-defined covert and clinical infarcts (i.e. all incident infarcts) in individuals with a recent ESUS.⁵⁰ The primary analysis will be performed on an ITT population (i.e. all patients with baseline and follow-up MRIs, including those with early study drug discontinuation), based on the assessment by an MRI Core facility. An additional analysis will be performed on patients with baseline and follow-up MRIs who take study drug until the efficacy cutoff date.

Secondary objectives will be to determine the effect of rivaroxaban compared to aspirin for reducing covert infarcts, the progression of volume of white matter hyperintensities (WMH), functional decline (SAGE), and cognitive decline (MoCA) in the patients with recent ESUS enrolled in this substudy.⁵¹

Exploratory objectives will be to determine the imaging profile which predicts clinical recurrence as well as the radiologic pattern of recurrent lesions, and to evaluate the predictors of covert infarcts at baseline in the ESUS population.

Approximately 1000 patients will be enrolled in this substudy that is designed to detect a 35% reduction in covert strokes by rivaroxaban with 80% power and a two-sided alpha of 0.05, assuming an annual covert stroke rate of 10% in patients receiving aspirin, a mean follow-up of 24 months, and a drop-out rate of 15%.

The substudy will be conducted at sites with access to 1.5 or 3Tesla MRI. Patients with no contraindication to MRI as assessed using local institutional protocols, e.g., claustrophobia, metal-containing devices or foreign bodies, will be enrolled.

Two MRIs will be required⁵²:

- Baseline: within 7 days of randomization if the patient is randomized within 30 days of the index event or from 7 days before to 30 days after randomization, if the patient is randomized >30 days after the index event. The MRI for the index event may qualify as the baseline MRI, if the imaging was performed within 7 days before randomization. In the event of a technically unsatisfactory scan as determined by the core laboratory, the site will have 30 days from notification by the coordinating center to repeat the scan.
- Follow-up: within 30 days of EOT visit in individuals who have not experienced a symptomatic stroke prior to EOT or within 30 days of a symptomatic stroke.

If a recurrent stroke occurs, all information on MRI or CT performed as routine diagnostic will be collected.

Detailed information regarding image acquisition and processing will be found in an MRI Imaging Manual.

⁵⁰ The primary endpoint was revised with global Protocol Amendment 5 to allow a more sensitive analysis for the entire study population. See Section 13.1.2 for details.

⁵¹ The secondary endpoint was revised with global Protocol Amendment 5 accorded to the revised primary endpoint. The reference to DSS was also removed.

⁵² Additional guidance and clarifications were made to this paragraph with global Protocol Amendment 5. See Section 13.1 for details.

A pooling of data from this MRI substudy with substudy data from the ongoing COMPASS study is planned. The later COMPASS MIND MRI substudy will be conducted in 1500 patients with coronary and peripheral artery disease, who receive either aspirin 100 mg o.d., 5 mg rivaroxaban b.i.d., or 2.5 mg rivaroxaban b.i.d. plus aspirin 100 gm o.d.. The 2 substudies will share the set-up, outcome definitions (MRI and cognitive), and MRI Core Facility.

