5.2 Discontinuation of patients from study treatment - amended

An excessive rate of patient discontinuations from either treatment or “drop-outs” from the study may render the trial non-interpretable. In this study, outcome events and vital status data are crucial to the primary analysis and must be collected until the end of the study, even if patients are no longer taking study medication. **Therefore, all efforts will be taken to**

¹⁹ Criterion revised with global Protocol Amendment 5. See Section 13.1 for details.

motivate patients to comply with all study procedures and to continue to be followed until the end of the trial.

Patients may discontinue study medication at their own request and without giving reasons (even though providing a reason is encouraged), based on the investigator's judgment, if the patient is pregnant, or at the request of the sponsor (exceptional circumstances). In case a patient is diagnosed with atrial fibrillation with an episode of at least 6 minutes during the study trial medication must be stopped (see section 6.9.2).²⁰ **Study drug will not be routinely discontinued in participants reaching a potential outcome event unless there is a safety concern or a clear indication for an alternative antithrombotic therapy as determined by the local investigator.**

In case of a temporary study medication interruption²¹ for any reason, study medication will be restarted as soon as medically justified in the opinion of the investigator. There is no defined maximum limit for temporary treatment interruption.

For all patients who permanently discontinue study medication, the patients will still be part of the study, and outcome events and vital status must be reported until the efficacy cut-off date for the study is announced. All safety data will continue to be collected for 1 month after the last study medication intake (safety follow-up visit). The investigator and patient must discuss and determine further follow-up options. Options for follow-up are listed below, in descending order of preference:

1. Patient continues the regular study clinic visits at the investigator's site as outlined in the protocol
2. Patient will be contacted by phone at the regular follow-up intervals
3. Patient allows his/her general practitioner or a family relative to be contacted (if allowed in respective country) at the regular follow-up interval
4. Patient will be contacted once at the end of the study

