If a patient is diagnosed with AF during the study that requires oral anticoagulation according to the investigator's judgment, the patient will stop double-blind study medication. Per protocol, study medication must be permanently discontinued if AF is seen in a 12-lead ECG or if an AF episode of ≥ 6 minutes is identified during cardiac monitoring.²⁷ The patient will be offered open-label rivaroxaban according to the local label (if acceptable by local regulations) or alternatively, the investigator may prescribe other standard of care e.g., VKA. If the patient is switched to a VKA, adequate anticoagulation during the initiation phase needs to be ensured according to the Xarelto[®] Summary of Product Characteristics, due to the length of time required to achieve therapeutic anticoagulation with VKAs.

Patients receiving open-label rivaroxaban will continue with the regular study visits. For patients treated differently, the instructions for permanent discontinuation of study medication as outlined in Section 5.2 should be followed.

6.9.3 Guidance for management of participants who have coronary artery disease identified during the study

Patients diagnosed with coronary artery disease (CAD) during the study and in whom treatment with dual antiplatelet therapy is warranted (e.g., after percutaneous coronary intervention [PCI]) will interrupt study medication for the duration of dual antiplatelet therapy, as the combination of dual antiplatelet therapy and rivaroxaban 15 mg may lead to an increased bleeding risk. Study medication will be restarted once dual antiplatelet therapy is stopped.

For patients in whom treatment with ASA is recommended (e.g., stable CAD) the investigator can consider continuing study medication with non-study ASA only if the dose of ASA is ≤ 100 mg daily. Use of higher doses of ASA will require interruption of study medication.

6.9.4 Guidance for management of participants who have a recurrent ischemic stroke during the study

For patients who have a recurrent ischemic stroke during the study, a complete diagnostic work-up including brain imaging, at least 24-hour cardiac rhythm monitoring, and echocardiography is encouraged. All available clinically-obtained diagnostic results will be recorded on eCRFs for the purposes of event adjudication and secondary analyses.

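### The MRI substudy's additional on-drug analysis drops a patient who stops drug after an on-drug clinical infarct, although the endpoint is already recorded

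*Protocol*

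**What the plan says.** Protocol 14.1.1 sets the substudy's primary objective as the effect on "MRI-defined covert and clinical infarcts (i.e. all incident infarcts"). Its primary analysis takes "all patients with baseline and follow-up MRIs, including those with early study drug discontinuation". The additional analysis is limited by continued drug use: "An additional analysis will be performed on patients with baseline and follow-up MRIs who take study drug until the efficacy cutoff date".

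For a patient with a symptomatic stroke the same section does not wait for the end of treatment: the follow-up MRI is due "or within 30 days of a symptomatic stroke".

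Three other parts of the Protocol bear on whether drug is stopped after an infarct:

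- Section 5.2: "Study drug will not be routinely discontinued in participants reaching a potential outcome event unless there is a safety concern or a clear indication" for another antithrombotic.
- Section 6.9.4 encourages a full work-up after a recurrent ischemic stroke, including at least 24 hours of rhythm monitoring. It also allows emergency unblinding for thrombolysis decisions.
- Section 6.9.2: "study medication must be permanently discontinued if AF is seen in a 12-lead ECG", or if monitoring shows an episode of 6 minutes or more.

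The main trial's on-treatment scope (Protocol 8.2.3, SAP 4.5.2) counts outcome events from randomization until 2 days after permanent discontinuation. The SAP has no section on the MRI substudy.

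**The concern.** An on-drug analysis should describe infarcts that arise while patients are taking the drug. Here the restriction runs past the endpoint. Once a clinical infarct has occurred and the follow-up scan is done, the patient's outcome is settled, yet the patient stays in the analysis only by continuing drug until the efficacy cut-off, possibly much later. Clinical infarcts, unlike covert ones, come to attention and can lead to stopping, so endpoint events are exposed to a removal route that event-free patients do not share.

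At stake are the absolute infarct risks in this analysis and, if stopping after a stroke differs between arms, the risk ratio. A difference is possible because treatment can be unblinded after a stroke, but the documents do not say that one is expected.

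**Working it through.** **Step 1. The plan's own figure.** Section 14.1.1 gives about 1000 patients, 10% covert strokes per year on aspirin, a 35% reduction, 24 months, 15% drop-out, 80% power and two-sided 0.05.

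- Evaluable: 1000 × 0.85 = 850, or 425 per arm.
- Two-year covert risks: 2 × 10% = 20%, and 20% × 0.65 = 13%.
- n per arm = [1.96√(2 × 0.165 × 0.835) + 0.842√(0.20 × 0.80 + 0.13 × 0.87)]² / 0.07² = 441, so 882 evaluable and 882 / 0.85 = 1038 enrolled. Power at 425 per arm is 78.6%.

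This is close to the stated design, which is not in dispute. It supplies inputs for Step 3.

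**Step 2. One patient under three rules.** A patient has a symptomatic infarct on drug, has the follow-up MRI on time, and is then found to have AF and stops permanently.

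- Substudy primary analysis: included, with the infarct counted.
- Main trial on-treatment scope: event counted, because it precedes discontinuation.
- Additional substudy analysis: excluded, because drug was not taken until the cut-off.

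No exception is written for this patient.

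**Step 3. Size.** Inputs:

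- Clinical risk c over two years, from 3.8% per year on aspirin and a 30% reduction (Protocol 8.6): 1 − exp(−0.076) = 7.32% and 1 − exp(−0.0532) = 5.18%. At 425 per arm that is 31.1 and 22.0 patients. The rate is an upper proxy, because the main endpoint also includes hemorrhagic stroke and systemic embolism.
- Covert risk k: 20% and 13%, taken as independent of clinical infarct.
- Share r of patients without a clinical infarct still on drug at two years, from 10% and then 7% discontinuation (Protocol 8.6): 0.90 × 0.93 = 0.837.
- Share p of patients with a clinical infarct who are not on drug until the cut-off: **not in the documents; assumed**.

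With nobody removed, all-infarct risk is c + (1 − c)k = 25.85% and 17.51%, ratio 0.677.

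In the on-drug set:

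- clinical risk = c(1 − p) / [c(1 − p) + (1 − c)r]
- all-infarct risk = [c(1 − p) + (1 − c)rk] / [c(1 − p) + (1 − c)r]

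For aspirin with p = 30%: (0.0512 + 0.1551) / (0.0512 + 0.7757) = 24.96%.

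| p aspirin / p rivaroxaban | Aspirin clinical % | Aspirin all % | Rivaroxaban all % | All-infarct ratio |
|---|---|---|---|---|
| 10 / 10 | 7.83 | 26.26 | 17.83 | 0.679 |
| 16.3 / 16.3 | 7.32 | 25.85 | 17.51 | 0.677 |
| 30 / 30 | 6.19 | 24.96 | 16.80 | 0.673 |
| 50 / 50 | 4.50 | 23.60 | 15.75 | 0.667 |
| 100 / 100 | 0 | 20.00 | 13.00 | 0.650 |
| 30 / 15 | 6.19 | 24.96 | 17.57 | 0.704 |
| 15 / 30 | 7.42 | 25.94 | 16.80 | 0.648 |
| 50 / 25 | 4.50 | 23.60 | 17.06 | 0.723 |
| 25 / 50 | 6.61 | 25.29 | 15.75 | 0.623 |

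Patients with a clinical infarct who are removed (31.1 and 22.0 times p): 3.1 and 2.2 at 10%, 15.6 and 11.0 at 50%.

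The turning point is p = 1 − 0.837 = 16.3%. Above it the risks are understated; below it they are overstated.

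**The case against.** The strongest reply is that little is likely to happen. Section 5.2 states the rule first: drug is not routinely stopped after a potential outcome event. Rhythm monitoring after a stroke is encouraged, not required, and the sample-size section assumes only about 5% of patients switching for AF over the study. This stands. A reader might infer from the AF pathway that stopping after a stroke is likely, but the documents show only that it is possible, and nothing in them supports 30% or 50%.

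Other stronger readings also go too far:

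- The ratio for clinical infarcts alone would move much more (at 50% v 25%, 4.67 / 4.50 = 1.04 against 5.18 / 7.32 = 0.71). That is not the substudy endpoint, and the unequal stopping is an assumption.
- A reader might conclude that risk is always understated. At 10% stopping it is slightly overstated.
- A reader might expect the planned pooling with the other MRI substudy to carry the problem forward. Section 14.1.1 says data will be pooled; it does not say that this population will be used.

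It is also fair that any analysis of patients who complete treatment selects on later events, and that this one is only supplementary. That limits the importance. It does not explain why the substudy departs from the trial's own on-treatment rule.

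**Conclusion.** The point holds as one of logic: as written, the on-drug set depends on drug use after the endpoint, and the SAP does not repair it. The consequence is modest. Under the assumptions above, the all-infarct ratio stays within about 0.01 of 0.677 when up to half of stroke patients stop in both arms. It shifts by about 0.03 in either direction at 30% v 15%, and by about 0.05 at 50% v 25%. Absolute risks are understated only if patients with a clinical infarct stop more often than others. The direction of any bias in the comparison cannot be stated, because the documents give no stopping rate by arm.

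The substudy's primary analysis keeps early discontinuers and does not have this defect. The change is worth making, but no main conclusion rests on it.

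**What to change.** In Protocol 14.1.1 or a substudy analysis plan, replace the single on-drug restriction with two rules.

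1. Clinical infarcts: analyze time from randomization to first clinical infarct under the trial's on-treatment scope, counting events until 2 days after permanent discontinuation and censoring at last dose plus 2 days. Stopping after an infarct then never removes the patient.
2. Covert infarcts, which have no onset date: assess them in patients without a clinical infarct who stayed on drug until the EOT visit in the trial close-out window. Name that visit explicitly, because under section 7.1.2.4 a patient who discontinues early may have an EOT visit after stopping.

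If a single all-infarct proportion is also reported, state its downside: event-free patients must stay on drug longer than patients with an event, so events are slightly over-represented. With strokes spread evenly over two years, mean retention at the stroke is the average of (1 + 0.90)/2 and (0.90 + 0.837)/2, or 0.909. Using 0.909 in place of 1 − p, aspirin clinical risk is 7.90% against 7.32%, and the all-infarct ratio 0.679 against 0.677. If rivaroxaban discontinuation were doubled to 20% and then 14% (an assumption), r is 0.80 × 0.86 = 0.688, retention at the stroke is 0.822, rivaroxaban all-infarct risk is 18.33%, and the ratio is 18.33 / 26.32 = 0.70. The proportion is therefore sensitive to discontinuation that differs by arm.

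The cost is a few sentences and a small derivation. Dose, event and scan dates are already needed for the trial, and no visit, scan or treatment rule changes.
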